#### 3.5 Recruitment and enrollment of participants

We will use the database of a baseline study conducted to determine the prevalence of Metabolic Syndrome in Wakiso district (Manuscript under peer review) as our source of participants. Those participants who were diagnosed with MetS will be recruited into the study.

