#### **3.0 DESIGN AND METHODS**

#### 3.1 Study Design:

The study design is an Individual Randomized Parallel-Group Trial study with both an intervention group and a control group in Wakiso district, Central Uganda. All women with Metabolic Syndrome identified in our baseline study will be randomized to either intervention and control groups. The intervention will be administered in 5 groups of 12 participants.

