#### **3.4 Study Participants:**

Female aged 15-49 years with Metabolic Syndrome in Wakiso district.

The intervention group participants will be women identified in Wakiso district during our baseline study. The intervention group will receive group nutritional education, group physical activity, and motivational interviewing. The control group also with Metabolic Syndrome identified in Wakiso district in the baseline study will receive usual standard of care.

**Inclusion Criteria:** Being a female aged 15-49 years in Wakiso district, Central Uganda with metabolic syndrome (defined by the 2009 Joint Interim Statement (JIS)), living in the community for at least one year, able to provide informed consent (oral or written), including consent for a follow-up interview 3 months after the start of the study. Participants under 18 years, should be able to provide assent and get informed consent from their parent /guardian or legal representative.

**Exclusion Criteria:** Females with chronic diseases such as liver, kidney, heart diseases or any diseases that could be worsened or affected by intervention sessions, participants on a prescribed diet plan, and those with the potential to undergo any surgical procedure during the intervention period.

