#### Sample selection

**Sampling Procedure:** A purposive sample of females with Metabolic Syndrome in Wakiso from the baseline study undertaken in Wakiso district will be followed up in the community, screened and invited for participation in the study at baseline.

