#### **Randomization: Allocation Concealment**

Random allocation will be conducted with minimization algorithm centrally in a single step to obtain two lists of nominative data. The allocation concealment will be by sealed opaque envelop to preserve allocation concealment. The biostatistician will assign numbers to the envelopes from 1 to 120. This will help prevent the possibility for researchers to predict or influence the allocation of participants. Due to practical reasons, we shall obtain informed consent after the randomization process.

The study coordinator who will be blinded to the randomisation allocation list will enrol the participants. The numbered envelopes will be distributed in sequence from 1 to 120 to a list of names from the baseline survey diagnosed with Metabolic Syndrome. This list of names will be generated after randomisation of those names.

All the individuals belonging to the intervention group will be separated from the individuals belonging to the control group and two allocation lists will be generated with control and intervention groups. The principal investigator will then follow up and identify the study participants in their respective villages, with the assistance of the village chairpersons.

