# 3.9 Data Collection and Management:3.9.1 Data collection tool

To ensure consistency and minimization of errors in the data collected, standardized methods of data management will be used by the study team.

**Data Collection Procedures:** Base line data will be collected from study participants in the intervention and control group. This will be before the introduction of the intervention. At baseline data collection, informed consent, questionnaires on comprehensive medical history, dietary intake, smoking and alcohol intake, medication use, physical activity, anthropometry, BP, FBS and lipid profile tests will be undertaken for all participants.

After the introduction of the intervention, data will be collected serially from study participants in the intervention arm on selected variables before the group sessions to monitor adherence of participants to the intervention. Final end-line data similar to data collected at baseline will be collected in both the intervention and non-intervention arms. In control group, the participants who have baseline data will be considered in analysis for comparison purposes.

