#### **3.10 Ethical Considerations**

Approval will be sought from by the MakSPH Higher Degree's Research and Ethical Committee (HDREC) and Uganda National Council of Science and Technology (UNCST). All participants will be informed about the purpose of the study and the use of resulting data. Consent will be obtained from all respondents. All participants will sign a voluntary informed consent form for being included study. Assigned copy of the informed consent will be given to each participant after the interview. For participants under 18 years, we will seek consent of their legal guardians and assent of the participants.

Confidentiality will be always observed by only allowing investigators to access the data. Electronic or hard copies of data will be stored securely. Anonymity of respondents will be ensured by using codes as identifiers.

Participants in intervention group will be informed about the risks associated with intervention including discomfort of finger prick and venepunctures, possible discomfort and dizziness following physical activity. The study team will ensure that participant safety, privacy and confidentiality are ensured during the intervention sessions.

The participants in the control group will be given information about the principles of a healthy lifestyle from study team.

Female nurses and female graduate medical students will conduct waist circumference measurements. Qualified laboratory technicians will conduct finger pricks and venipunctures.

All newly detected NCD patients will be given a referral form to attend the nearest health center for further management.

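### Women are randomised from an earlier survey's MetS list before the trial's own baseline measurements, and nothing says how an allocated woman who no longer has MetS is handled

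*Protocol*

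**What the plan says.** The population is tied to a previous survey in several places. Section 3.1: "All women with Metabolic Syndrome identified in our baseline study will be randomized to either intervention and control groups". Section 3.5 names the survey database as the source and adds "Those participants who were diagnosed with MetS will be recruited into the study". The survey manuscript is described there as already under peer review, so the qualifying measurements predate the trial. The interval is not given.

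The order of events is in section 3.7, Randomization: Allocation Concealment. Numbered envelopes are distributed "to a list of names from the baseline survey diagnosed with Metabolic Syndrome". The same section states that "we shall obtain informed consent after the randomization process". Two allocation lists are drawn up, and the principal investigator then traces the women in their villages.

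Three places bear on whether MetS is checked again:

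- Section 3.4 makes MetS by the 2009 JIS definition an inclusion criterion, without saying on which measurements.
- Section 3.7, Sample selection, says survey women will be followed up, "screened and invited for participation in the study at baseline". What the screening contains is not stated.
- Section 3.9.1 says "Base line data will be collected from study participants in the intervention and control group", before the intervention starts. It lists anthropometry, blood pressure, fasting glucose and a lipid profile, which cover all five components.

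No section makes the trial-visit result a condition of being randomised, or says what happens to an allocated woman who does not meet the definition at that visit.

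**The concern.** Section 3.6 defines MetS as at least three of five threshold crossings. Women selected because they crossed on one occasion will partly fall back when measured again, even with no true change. Some may also have changed since the survey.

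A woman without MetS at the trial visit has no MetS for the programme to reverse. Such women lower the 3-month prevalence in both arms, shrink the absolute difference, and move both proportions towards the middle of the scale, where the variance is larger. Section 3.7 plans for a difference of 0.20 and makes no allowance for this.

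The other possibility is that the screening does re-test MetS and negative women are removed. In the stated order they would be removed after allocation, under no written rule, from groups whose contact and consent also came after allocation. That puts the comparability of the arms at risk.

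**Working it through.** **Inputs from the protocol (section 3.7).** Significance level 5%, power 80%, between-group difference 0.20, total 98 before the design effect, 104 after it, 120 finally, 1:1 allocation.

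**Inputs that are assumptions.** The two prevalences behind the 0.20 are not given. Nor is f, the share of survey-positive women who are negative at the trial baseline; 0 to 30% is shown. Nor is r, the probability that such a woman is positive at 3 months; 0 and 0.4 are used, the same in both arms.

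**Step 1: reproduce 98.** Two-sided test, pooled null variance, p̄ the mean of pc and pt:

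n per arm = [1.96·√(2p̄(1−p̄)) + 0.842·√(pc(1−pc) + pt(1−pt))]² / (pc−pt)²

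With pc = 0.95 and pt = 0.75: [1.96·√0.255 + 0.842·√0.235]² / 0.04 = 48.8, so 49 per arm and 98 in total. This pair is not unique. 0.25 vs 0.05 gives the same total, 0.90 vs 0.70 gives it one-sided, and 0.94 vs 0.74 gives it with unpooled variance. In a population selected for MetS, the high-prevalence pairs are the plausible ones.

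**Step 2: dilution.** The 3-month prevalences become pc(1−f) + rf and pt(1−f) + rf, so the difference is 0.20(1−f) whatever r is.

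**Step 3: power at n per arm.** With d the diluted difference:

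Φ{[d√n − 1.96·√(2p̄(1−p̄))] / √(pc(1−pc) + pt(1−pt))}

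Example, f = 0.20, r = 0, n = 49: the prevalences are 0.76 and 0.60, d = 0.16 and p̄ = 0.68. Then (1.12 − 1.293)/0.650 = −0.266, and power is 40%.

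| f | Difference | Power, 49 per arm (r = 0 to 0.4) | Power, 60 per arm (r = 0 to 0.4) |
|---|---|---|---|
| 0 | 0.20 | 80% | 88% |
| 5% | 0.19 | 67–71% | 76–79% |
| 10% | 0.18 | 56–62% | 65–71% |
| 20% | 0.16 | 40–46% | 47–54% |
| 30% | 0.14 | 29–33% | 34–40% |

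Sixty per arm is the best case, with no losses. The figures ignore the design effect and the exclusion of women attending under 60% of sessions.

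**Step 4: confirmed women can also fall back.** One confirming visit does not stop later reversion, so 0.95 in confirmed controls may be too high. With an assumed 0.86 vs 0.66 and 49 per arm, power is 64% at f = 0 and 37–40% at f = 20%.

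**Step 5: size of the remedies.** Women to screen for 120 confirmed places, 120/(1−f): 134, 150 and 172 at f = 10%, 20% and 30%. If allocation stays first and only confirmed women are analysed, f = 20% leaves 49 × 0.8 ≈ 39 per arm, with power of about 71% under 0.95 vs 0.75.

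**The case against.** The strongest reply is that the protocol does provide for a check: women are screened, JIS MetS is an inclusion criterion, and every component is measured again before the intervention. This stands in part. A reader might infer that MetS is never re-confirmed and that women without it will certainly be enrolled. The text does not support that. It leaves the content and consequence of the screening open, and it places allocation ahead of it.

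A second reply is that the primary outcome is a between-group one. Fall-back occurs in both arms and cancels on average. This also stands. A reader might fear that a spontaneous fall would pass for a treatment effect, but only a within-arm reading would be misled, and the control arm guards against that.

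A third is that the starting point for change is clear enough. Section 3.6 measures outcomes before and at the end of the activities, and section 3.9.1 places baseline data collection before the intervention. No section uses survey values as the starting point. The word baseline serves for both the survey and the trial visit, but this is a matter of wording.

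Finally, the size is assumed. The protocol gives no survey prevalence, visit-to-visit variation or interval. Under section 3.6, treatment or known diabetes keeps a component positive whatever the reading, which limits reversion. Section 3.10 says "All newly detected NCD patients will be given a referral form to attend the nearest health center for further management", but it does not say that survey women were referred earlier, so change through referral is a conjecture. These points limit the figures to an illustration. They do not answer the order of events.

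**Conclusion.** The point holds in this form. Names are allocated on an earlier survey diagnosis, before contact, consent and the trial's own measurements. Any re-check therefore follows allocation, and the handling of a woman found negative is not specified.

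If all randomised women are kept, the consequence is a smaller absolute difference, about 0.20(1−f), and lost power, not a false positive. Under 0.95 vs 0.75 at 49 per arm, a 10% negative share takes power from 80% to 56–62%, and 20% takes it to 40–46%. These figures rest on assumed prevalences and an assumed f. The direction does not depend on the particular values. The gain from confirmation should not be read as a return to 80%: under 0.86 vs 0.66 it is 64% against 37–40% at f = 20%. If negative women are instead dropped after allocation, comparability of the arms is in question as well.

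**What to change.** In sections 3.4, 3.5 and 3.7 (Sample selection and Allocation Concealment), reverse the order. Use the survey list only to find women to screen. Take consent and the baseline measurements already planned in section 3.9.1, classify by the JIS criteria on those results, and assign the next envelope only to women who meet them. In section 3.6, state that baseline means this visit. In section 3.7, state the two prevalences behind 98.

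The cost is a short wait for laboratory results and full baseline visits, including fasting bloods, for some women who are not then randomised: about 134 to 172 screened for 120 places at 10–30% negative. Section 3.1 already randomises every survey case, so a surplus may not exist and fewer than 120 may be reached.

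If allocation must stay first, report all randomised women and prespecify an analysis of those MetS-positive at the trial baseline visit. State its smaller size (about 39 per arm and 71% power at 20% negative under 0.95 vs 0.75). State also that attendance at that visit may differ by arm, because consent follows allocation; blinding the assessors does not remove this.

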#### 3.6 Outcomes of interest:

#### **Primary outcome**

The primary outcome will be the between–group change in MetS prevalence after 3 months from start of intervention.

The 2009 Joint Interim Statement (JIS) will be used to diagnose MetS, defined as the presence of  $\geq$  3 of the following 5 factors: increased WC (women:  $\geq$  80 cm), low HDL-C (women: <50 mg/dl (1.3 mmol/l) or treatment of low HDL-C), Hypertriglyceridemia  $\geq$ 150 mg/dl (1.7 mmol/l) or treatment, elevated BP (systolic BP  $\geq$  130 mmHg and/ or diastolic  $\geq$ 85

mmHg or treatment for hypertension) and elevated fasting blood sugar (FPG  $\geq$  100 mg/dl (5.6 mmol/l) or diabetes mellitus or treatment[3]

The European cutoffs for waist circumference will be used as recommended by WHO because of the unavailability of population/country specific WC cutoffs for sub-Saharan Africans [3] or Uganda.

#### Secondary outcomes

The secondary outcome will be the within - and between group variations in each of the following variable measured.

- dietary habits and behaviors (salt intake, fruits and vegetables intake, fat intake,
- anthropometric (weight, WC and BMI)
- cardio-metabolic (hypertension, blood glucose, triglycerides, HDL)
- nutrition knowledge
- lifestyle (physical activity, alcohol intake, cigarette smoking)

Mean change in parameters across the comparison and intervention groups will be determined. The measurement of the outcomes will be conducted before and at the end of the activities to determine the effect of the intervention.

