#### 2.2.2 Secondary objective

• To determine the effect of nutrition education, physical activity and motivational interviewing intervention on metabolic syndrome outcomes (blood pressure, high-density lipoprotein cholesterol, triglycerides, fasting blood sugar, waist circumference) and dietary intake, physical activity among females aged 15-49 years with metabolic syndrome in Wakiso district.

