#### Socio-demographic characteristics

A standardized interviewer-administered questionnaire will be adopted to obtain data on socio-demographic factors, behavioral factors (smoking status, alcohol intake, physically active or not) and history of NCDs like Diabetes, hypertension, obesity and dyslipidemia. A questionnaire will be administered for analysis of the daily consumption and type of foods eaten at breakfast, or as snacks, at lunch and super.

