#### **Data Analysis**

The data for participants who attend less than 60 % of their respective intervention sessions will be excluded from analyses.

Participants with attendance rates below 60% in the intervention sessions will not be included in the analyses.

The analyses will be conducted using Stata statistical software (SE/ 14.0, StataCorp, College Station, TX, USA. Variables will be expressed using descriptive analysis (means and SD). The baseline information for both comparison and intervention groups will be statistically compared regarding all influencing factors at baseline and end line (12 weeks). The chi-square test will analyse for differences in categorical outcomes, including baseline study characteristics, metabolic risk factors (waist circumference (WC), blood pressure (BP), triglycerides, fasting blood sugar(FBS), and high-density lipoprotein (HDL) Cholesterol),

and other factors including dietary habits such as fruits and vegetable intake, and food groups consumed. Behaviours, including smoking, alcohol intake, and physical activity, will also be analysed.

The Student T test for independent samples and variance analysis (ANOVA) will compare cardio-metabolic parameters (and their variations - to find any differences between findings) between the intervention group and the comparison group at the baseline and end of the intervention (after-before).

A 2 factor (2 x 2; group x time) repeated measures analysis of variance (ANOVA) will be performed for each dependent variable and a 1-way ANOVA will be used to assess the significance of differences between groups on the dependent variables assessed. Tukey's post hoc analysis will be performed if there is a significant finding. The T test for paired data will be applied to investigate within –group variable variations (after-before). Statistical significance will be set at p < 0.05.

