Linear relationships will be estimated using Pearson correlation (crude model) to examine the associations between changes in variables, expressed as percentage of change ((endpoint - baseline value)/baseline value × 100). A multilevel generalized linear mixed model (GLMM) will be performed to identify the contribution of changes in time /round (baseline, end-line) and group (control, intervention) to changes in metabolic parameters (BP, WC, HDLC, FBS and Triglycerides) independent of other factors (education level, age, occupation etc). The model allows for the analysis of data with repeated measures, particularly baseline and end-line measurements for each individual. It also assesses the effects of the intervention and accounts for the correlation between observations within individuals due to repeated measures, as well as the clustering of individuals within the control and intervention groups.

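### Blood pressure is named two ways as a secondary outcome, and the metabolic syndrome components are tested both as categories and as values with no deciding analysis

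*Protocol*

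**What the plan says.** **Which blood pressure variable.** Protocol section 2.2.2 gives the secondary targets as "metabolic syndrome outcomes (blood pressure, high-density lipoprotein cholesterol, triglycerides, fasting blood sugar, waist circumference", a list of measured quantities. The Secondary outcomes part of section 3.6 lists instead "cardio-metabolic (hypertension, blood glucose, triglycerides, HDL". The same part adds: "Mean change in parameters across the comparison and intervention groups will be determined". The mixed model under Data Analysis is for "changes in metabolic parameters (BP, WC, HDLC, FBS and Triglycerides", so blood pressure is again a parameter.

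**Which cut-off.** The primary outcome text in section 3.6 defines elevated blood pressure, as one of the five metabolic syndrome components, as 130 mmHg systolic and/or 85 mmHg diastolic, or treatment. Nothing says that this rule defines the secondary outcome *hypertension*.

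**Which test.** Data Analysis states: "The chi-square test will analyse for differences in categorical outcomes, including baseline study characteristics, metabolic risk factors (waist circumference (WC), blood pressure (BP", and the list goes on to triglycerides, fasting sugar and HDL. The sentence before it has the groups "statistically compared regarding all influencing factors at baseline and end line (12 weeks", so the chi-square is not confined to a baseline table. The section also plans independent t tests and ANOVA on cardio-metabolic values and their changes, a 2 x 2 repeated-measures ANOVA for each dependent variable, a one-way ANOVA and the mixed model. One significance level, p < 0.05, serves all of them.

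**The concern.** The components are the substance of the secondary objective. For blood pressure the outcome list names a diagnosis where the objective and the model name a level, and it then asks for a mean change, which a yes/no diagnosis does not have in that sense. For all five components, both a categorical and a value-based between-arm test are planned at 5%, with no ranking.

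The two forms answer different questions, differ in power and often disagree. If the form to be cited is not fixed beforehand, the chance of a false claim per component exceeds 5%, and whether a component is reported as improved can depend on which test is quoted.

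**Working it through.** **1. The plan's own figures.** The sample size in section 3.7 (98, then 104, then 120) is for metabolic syndrome prevalence. No calculation is given for any component, so there is no stated figure to reproduce here. The size below rests on assumptions.

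**2. Inputs.** From the protocol: 60 women per arm, 10% dropout and failure to consent, hence 60 x 0.90 = 54 per arm; 130 mmHg systolic as the cut-off; two-sided 5% taken for each test. Assumed, because the protocol gives no values: mean systolic pressure 125-130 mmHg, SD 16 mmHg, baseline-endline correlation 0.6, normal distributions, and a true effect of 0 or -8 mmHg. Diastolic pressure and the treatment criterion are left out.

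**3. Value-based tests at -8 mmHg, by formula.** Standard error of the difference between arms:
- change score: 16 x sqrt(2 x (1 - 0.6)) x sqrt(2/54) = 2.75; 8/2.75 = 2.90; power = Φ(2.90 - 1.96) = 83%
- baseline-adjusted endline: 16 x sqrt(1 - 0.6²) x sqrt(2/54) = 2.46; 8/2.46 = 3.25; power = Φ(3.25 - 1.96) = 90%

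**4. Chi-square at 130 mmHg at -8 mmHg, by formula.** With mean 130, the proportions at or above 130 are 50.0% and 30.9%, and power is about 53%. With mean 125 they are 37.7% and 20.8%, and power is about 49%.

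**5. Simulation.** I drew 20,000 trials per setting under the same assumptions. It agrees with these formulas to within about a point and gives the joint behaviour of the tests:

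| Quantity | Result |
|---|---|
| Power at -8 mmHg, chi-square at 130 mmHg | about 49-54% |
| Power at -8 mmHg, t test on change | about 82% |
| Power at -8 mmHg, endline adjusted for baseline | about 89% |
| Chi-square and change t test disagree, -8 mmHg | about 40-44% of trials |
| No effect: chi-square or change t test significant | about 8-10% |
| No effect: endline t or change t significant | about 9% |
| No effect: any of the three significant | about 11-12% |

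Ranges cover mean systolic pressure from 125 to 130 mmHg and repeated runs.

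**6. What the split adds.** The choice between category and mean change takes the error per component from 5% to 8-10%. The two value-based t tests alone already give about 9%, and adding the chi-square to them brings 2-3 points more. So the excess comes from having several undecided analyses, of which the chi-square is one.

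**The case against.** The best reply is that this is loose wording in secondary outcomes. The outcome list speaks of measured variables and of mean change, and blood pressure is measured with a digital monitor. Read with the objective and the model, *hypertension* is probably a label for blood pressure. Chi-square for categories and t tests for values is ordinary language, and the yes/no forms are the building blocks of the primary outcome. Ranking of secondary analyses and multiplicity across them may be left to a statistical analysis plan that is not shown.

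Much of that stands. It is fair that the likely intent is a level, and it would be wrong to say that the protocol offers no cut-off: the 130/85 mmHg rule is an obvious candidate, and only the link is missing. A reader might also take the questionnaire item on "history of NCDs like Diabetes, hypertension, obesity and dyslipidemia" to mean that the outcome is a diagnosis that cannot reverse in 12 weeks. That item is background data, and nothing connects it to the outcome.

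What does not fall away is that the protocol itself fixes two names for one outcome and commits to competing tests of the same components at baseline and end line. That is stated in the text, not deferred. Waist circumference is listed as anthropometric, so the t-test sentence may not reach it, but the repeated-measures ANOVA and the mixed model do.

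**Conclusion.** The point holds as a correction worth making to the secondary outcomes. Blood pressure is named inconsistently, and no deciding analysis is named for any component. Under the assumed values, choosing between the chi-square at 130 mmHg and the change t test gives about 8-10% error per component in place of 5%, or about 11-12% if an endline t test may also be cited. The two verdicts disagree in about 40-44% of trials at a true -8 mmHg. These sizes are illustrations for systolic pressure and move with the assumed mean, SD, correlation and effect.

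Three stronger readings are not supported:
- A figure of about 47% for at least one false positive across five components (1 - 0.88^5) assumes independence and lacks its comparator. Five single tests at 5% already give 1 - 0.95^5 = 23%, and that part is not due to this fault.
- Disagreement above about 44%, up to 54%, needs a 140 mmHg cut-off, which appears nowhere in the protocol.
- Removing the chi-square alone would not cure the problem, because about 9% per component remains from the two t tests.

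The definition and test of the primary outcome are not touched.

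**What to change.** **Section 3.6, Secondary outcomes.** Replace *hypertension* with systolic and diastolic blood pressure in mmHg, and align the mean-change sentence with the deciding analysis named below.

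**Data Analysis.** For each component, name one deciding between-arm analysis: the endline level adjusted for its baseline value. Label every other analysis of that component as descriptive or supportive: chi-square, t tests on levels and on changes, one-way and repeated-measures ANOVA, and the mixed model unless it is itself specified as the deciding model. Report the proportions beyond the section 3.6 cut-offs by arm, without a deciding p-value.

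**Cost.** The change is wording in the secondary outcomes and in the test and mixed-model paragraphs of Data Analysis. All the values are already collected at baseline and end line. The loss is a confirmatory p-value for the change in proportion abnormal. The gain, under the assumptions above, is one test per component at its nominal 5%, with power of about 89% at -8 mmHg against 82% for mean change and 49-54% for the chi-square.
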